4.0 Inclusion/Exclusion Criteria

This prospective pilot study will be conducted over a 24-month period and will enroll a total of 40 infants. Infants will be randomized in a 1:1 ratio to the two groups; randomization will occur within REDCap. Inclusion criteria are as follows: infants, 34 weeks or greater gestation, exposure to opioids and/or benzodiazepine medications for 5 days or more, beginning a stable wean, and maternal age of 18 or older as these individuals are able to consent for themselves (see Table 2). Exclusion criteria will be captured in the medical record as follows: hemodynamic instability, transfer to another facility prior to completion of the weaning regimen or death. Parents identified by health care providers in the PCICU will be approached by study providers ([name], [name], [name], [name], or [name]) in the PCICU. Project procedures will be described and if participants would like to enroll in the study, the consent process will be completed by study providers. Following informed consent, acupressure will be administered within 24 hours MCJCHV. Healthcare providers caring for these infants will be identified through the medical record and subsequent surveys sent through their VUMC email. No ethnic group will be targeted or excluded from this study.

Table 2: Inclusion and Exclusion Criteria

Inclusion	Exclusion
34 weeks gestational age to 1 year of age	Transfer to another facility prior to wean completion
Maternal age 18 or older	Re-escalation of care/Worsening Illness
English speaking	Death
Hemodynamically stable	

Exposure to opioid and/or benzodiazepine for 5 days or more	
---	--

5.0 Enrollment

A purposeful sampling technique will be utilized to recruit participants from MCJCHV as referred by healthcare providers caring for infants exposed to opioids and/or benzodiazepines for surgical procedures. Informational flyers (Appendix A) will be produced and provided by healthcare providers to parents interested in participating in the study and asked if they would like to be contacted by the PI or research team. At that time, parents may contact the PI, ask the PI to call them, or the PI will be available during the week (Monday-Friday) to discuss the study immediately following their discussion with their healthcare provider. Additionally, infants at risk for developing withdrawal may be identified by following the census in the PCICU. Daily monitoring of the PCICU census via the electronic medical record will be performed by the PI.

Previous infant studies, including a pilot feasibility study conducted by the PI at MCJCHV, have reported high retention rates of mother's that consent to acupuncture for the treatment of withdrawal but we are mindful of challenges in enrollment and retention (1, 23, 24, 28). Enrolled participants will remain in the study until cessation of opioid and/or benzodiazepine unless they are transferred to another facility (see Table 2 Exclusion Criteria) or parents voluntarily withdrawal. If an infant is transferred, acupressure will not be continued but surveys will be provided to assess satisfaction and acceptability (Aim 3). Healthcare providers will be identified through the medical record and surveys sent through their VUMC email.

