This **intervention pilot feasibility study** will assess the impact of auricular acupressure as an additional non-pharmacologic therapy for infants at risk for developing iatrogenic Withdrawal Syndrome (IWS) in the Pediatric Cardiac Intensive Care Unit (PCICU) of Monroe Carell Jr Children's Hospital at Vanderbilt (MCJCHV). We will recruit **40 healthy, 34 weeks gestational age or older infants** exposed to prolonged medications (greater than 5 days) for cardiac procedures that may cause withdrawal upon cessation such as opioids, benzodiazepines, or other sedative medications. Participants will receive the auricular acupressure in addition to the standard of care such as clustered nursing care, touch, position change, environmental controls, holding, and swaddling. Within 24 hours of implementing a weaning protocol, acupressure will be applied to three designated points of one ear following the NADA protocol acupuncture technique while also incorporating the Near-Term Infant (NTI) conceptual framework identified elements (see figure 3). Acupressure will be administered via stickers that are adhesive to the skin like a Band-Aid (see figure 1). These stickers include a vaccaria plant seed in the center that applies continuous light pressure on the designated points. This form of acupressure was selected as it is organic and does not contain metal which may interfere with emergency medical care such as imaging. After the initial 24 hours of application, stickers will be removed, the infant's skin will be assessed for any disruption such as bruising or discoloration, and the stickers will be rotated to the infant's other ear at the same NADA protocol auricular sites. Acupressure stickers will be removed and applied to the opposite ear every 48-72 hours until withdrawal symptoms improve (1). Withdrawal symptoms are measured every 6 hours with the enhanced Withdrawal Assessment tool (WAT) as part of the standard of care. Upon completion of the weaning regimen, infants with a score of less than or equal to 3 or less than 2 above baseline with no more than 2 rescue medication doses in 24 hours will have the acupressure removed.

Figure 1: Auricular Acupressure to NADA Protocol Sites

Acupressure Sticker	Auricular Application	NADA Protocol Points: Shen Men, Liver, Lung
		 
Key: ● - Hidden Points

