2.0 Rationale and Specific Aims

Sedative medications such as opioids and benzodiazepines are commonly administered to improve comfort of infants undergoing cardiac surgical procedures. Unfortunately cessation of these medications are commonly associated with onset of uncomfortable withdrawal as infants become physically dependent on these medications (29, 30). This condition is known as Iatrogenic Withdrawal Syndrome (IWS) and is further associated with impaired neurological development as well as prolonged mechanical ventilation and hospital stays (3-5, 31-33).

Infants with IWS experience a multitude of symptoms shared by other infant conditions that have been improved with acupuncture including tremors, hypertonicity, agitation, disrupted sleep, feeding difficulty, vomiting, diarrhea, temperature instability, tachypnea, and impaired weight gain (34-37). Treatments focus on non-pharmacologic adjuncts that support physiologic stability and prevent further developmental difficulties, prolonged hospital stays, and interrupted maternal bonding (9, 38, 39). These therapies include swaddling, position change, soothing touch, and environmental controls; however, *they have not traditionally included acupressure as a non-pharmacologic adjunct*. Although standard interventions are helpful, there remains a need to optimize these interventions and further reduce or prevent the use of medication.

Current evidence suggests that acupuncture is safe and beneficial for multiple conditions that impact neonatal and pediatric populations including withdrawal, yet this therapy remains underutilized as there is a lack of high-quality studies evaluating feasibility and therapeutic efficacy in the treatment of dependence (1, 10-24). A less invasive acupuncture therapy is acupressure, a technique that applies mild pressure via stickers, similar to Band-Aids, to designated body points rather than needle insertion to provide a therapeutic benefit.

Acupressure may serve as an additional *non-pharmacological adjunct to ease the severe discomfort of withdrawal in infants physically dependent on medications*.

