6.0 Study Procedures (Design)

6.1. Interventions.

Acupressure Administration (Aim1). All participants will receive the standard non-pharmacological treatment, which may include any variety of the following treatments: rooming in, soothing touch, swaddling, skin to skin, positioning, reduced stimulation, and sound machines, as needed and tolerated. These treatments are documented by nurses in the medical record. The essential characteristics for neonatal acupuncture (Figure 3) as guided by the Near-Term Infant conceptual framework (Figure 2) are included in the delivery of this acupressure protocol.

Within 24 hours of weaning medications, one of five specialty trained advanced practice providers will apply acupressure stickers to one ear (left or right depending on access to site) in accordance with the NADA protocol acupuncture technique. Application will occur at designated points including Shen Men, Liver, and Lung: in the room with the mother; and potentially during breast feeding, holding, skin to skin contact or bottle feeds. Administrators and nurses will document the activities of the infant during acupressure placement in the medical record. Stickers will remain in place for 24 hours.

At 24 hours, skin will be assessed, and stickers will then be rotated to the opposite ear every 48-72 hours if there are no adverse effects such as skin irritation. Should skin irritation be present after the 24-hour period, the sticker applied to the opposing ear will be removed in 12 hours and skin assessed. If skin irritation continues, acupressure will be discontinued, and the participant will be withdrawn from the intervention portion of the study. Parents and health care providers of the infant will still be provided surveys to assess satisfaction and acceptability of acupressure. If no skin irritation occurs, stickers may be rotated for these participants every 12 hours. Assessment of the ear skin will be documented at the time of acupressure removal in the medical record. In accordance with previous neonatal studies that applied auricular acupressure under these guidelines (48-72 hour acupressure placement), we do not anticipate skin irritation but will continue to monitor throughout hospitalization (1, 20, 28). Acupressure will be discontinued when withdrawal symptoms measure less than or equal to 3 or less than 2 above baseline with no more than 2 rescue medication doses in 24 hours. Study participants will

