receive the same assessments as non-participants and must meet the same weaning qualifications in line with the standard of care.

Acupressure Efficacy (Aim 2). As part of the standard of care, multiple metrics will be captured and compared among the intervention and control group. These include duration of opioid and/or benzodiazepine medications, duration of weaning phase, duration of mechanical ventilation, and hospital length of stay. To ensure appropriate opioid dosage comparisons, all opioid medications will be converted to morphine equivalents (mg/kg/patient); benzodiazepine medications and dosages will also be captured. Consistent with the current standard of care for infants treated in the PCICU the following assessments will be conducted: Withdrawal Assessment Tool (WAT-1) for Pediatric Withdrawal every 6 hours, Preschool Confusion Assessment Method for the ICU (psCAM-ICU) every 12 hours, Richmond Agitation-Sedation Scale (RASS) every 2-4 hours and Faces Legs Activity Cry Consolability Scale (FLACC) every 4 hours.

Acupressure Acceptability (Aim 3). Prior to discharge and after completion of the weaning protocol, parent(s) will receive the Client Satisfaction Questionnaire (CSQ8) to assess parental satisfaction of acupressure as an additional therapy. Staff and providers who cared for participants will also receive three brief electronic surveys via REDCap directly to their email prior to discharge. This survey will include 12 questions: Acceptability of Intervention Measure (AIM), Intervention Appropriateness Measure (IAM), and Feasibility of Intervention Measure (FIM) to evaluate acceptability of acupressure as a complementary therapy. Qualitative feedback back from healthcare providers and parents will be documented by administrators at time of acupressure application and skin assessment. Such feedback would include observations reported to the research team by healthcare providers or parents.

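### Participation ends when the drug stops, but other sections run past that point, and the end of withdrawal, dose and restart data collection is never defined

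*Combined protocol and SAP*

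**What the plan says.** Section 5.0 (Enrollment) sets the exit: "Enrolled participants will remain in the study until cessation of opioid and/or benzodiazepine unless they are transferred to another facility". Parental withdrawal is the other exit named there.

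Section 2.0 places the condition under study at that event: "Unfortunately cessation of these medications are commonly associated with onset of uncomfortable withdrawal as infants become physically dependent on these medications". The opening summary likewise describes drugs given "for cardiac procedures that may cause withdrawal upon cessation such as opioids, benzodiazepines, or other sedative medications".

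Treatment starts earlier. Section 6.1 says: "Within 24 hours of weaning medications, one of five specialty trained advanced practice providers will apply acupressure stickers to one ear". WAT-1 is recorded every 6 hours, psCAM-ICU every 12, RASS every 2 to 4 and FLACC every 4, all as standard of care. Neither Section 6.1 nor the assessment table in Section 10.0 says when their collection ends.

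Other provisions reach the end of the wean or go beyond it:

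- The opening summary keeps stickers rotating until symptoms improve. It ties removal to a score and a 24-hour limit on rescue doses: "Upon completion of the weaning regimen, infants with a score of less than or equal to 3 or less than 2 above baseline".
- The Aim 3 text in Section 6.1 times the parent survey: "Prior to discharge and after completion of the weaning protocol, parent(s) will receive the Client Satisfaction Questionnaire (CSQ8").
- Section 6.1 monitors skin for the whole hospital stay.
- Hospital length of stay is an Aim 2 outcome (Section 2.0; assessment table in Section 10.0).

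Section 10.0 plans descriptive summaries by arm on the intention-to-treat principle, with no formal between-group tests.

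**The concern.** The general exit rule coincides with the event that the protocol itself associates with onset of withdrawal. An infant may score low through the wean, receive the last dose, and then show withdrawal or delirium, need rescue doses, or be restarted on drug. Under a literal reading of Section 5.0 that infant has already left, and nothing elsewhere says these events are recorded.

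There is also a comparability problem. Duration of the wean is an Aim 2 outcome, and under this rule it also sets how long each infant is scored. If acupressure lengthens or shortens the wean, the arms are summarised over different windows. Section 10.0 says that these summaries will show data trends, and Sections 2.0 and 7.0 look ahead to efficacy studies measured by the same tool. A window that depends on the arm would carry over into the planning of those studies.

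**Working it through.** No design figure is involved. The plan gives 40 infants allocated 1:1, with no alpha, power, effect size or standard deviation, so there is nothing to reproduce. The check is a comparison of time points.

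**1. Time points relative to the last dose**

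| Item | Where stated | Position |
|---|---|---|
| Stickers first applied | Opening summary; 6.1 | Within 24 hours of the wean, so before the last dose |
| End of participation | 5.0 | At cessation |
| Onset of withdrawal | Opening summary; 2.0 | Associated with cessation |
| Sticker removal | Opening summary | Judged at completion of the wean; later if the threshold is not met |
| CSQ8 | 6.1 | After the wean, before discharge |
| Skin monitoring | 6.1 | Whole hospital stay |
| Length of stay | 2.0 (Aim 2); 10.0 | Needs data to discharge |
| WAT-1, psCAM-ICU, RASS, FLACC | 6.1; 10.0 | Frequency only, no end |

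The second row cannot be a complete end of participation if the fourth to seventh rows are carried out. An infant who has not met the removal threshold at the last dose could still be wearing the stickers after leaving the study.

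**2. What the literal rule does to the WAT-1 window**

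Let W be the days from the start of the wean to cessation. One score every 6 hours is 24 / 6 = 4 per day, so an infant has about 4 × W scheduled scores during the wean. Each day of difference in W moves the window by 4 scheduled scores. Because W is itself an outcome, the window may differ by arm. The plan makes no provision for scores, rescue doses or restarts after W.

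**3. What the and/or wording does**

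For an infant on both classes, let the opioid stop at time A and the benzodiazepine at time B. Section 5.0 can be read as exit at the earlier of A and B or at the later. Under the earlier reading, doses of the remaining drug between the two times drop out of total dose, exposure duration and wean duration. All three are Aim 2 outcomes.

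**4. Link to Aim 1**

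The retention benchmark in Section 10.0 is more than 80% through all assessment periods. It cannot be counted consistently until the end of the assessment period is fixed.

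**5. What is not lost**

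WAT-1 and the other scores run from the start of the wean, and Section 5.0 does not remove them.

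**The case against.** The strongest reply is that one retention sentence in the Enrollment section is being treated as the data-collection rule. Leaving does not end all collection: parents of transferred infants still receive surveys, skin is followed through the hospital stay, and length of stay needs data to discharge. The text on sticker removal implies further scoring of infants who miss the threshold at the end of the wean, and the reference to completion of the weaning regimen suggests that the whole wean is meant, not the first drug stopped. Infants must also meet the same weaning qualifications as non-participants, and Aim 2 is descriptive in a study whose main goal is feasibility.

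Much of this stands, and it rules out four stronger readings that a reader might infer:

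- **That no score after cessation will exist.** The plan contradicts itself, so such data are undefined, not definitely excluded.
- **That withdrawal goes unobserved.** Section 2.0 says that cessation is commonly associated with onset; it does not confine withdrawal to the time after the last dose. Withdrawal is treated and scored throughout the wean.
- **That failed weans fall outside the study.** An infant whose wean fails before cessation has not met the Section 5.0 exit. Any loss of such infants would come from the re-escalation exclusion in Section 4.0 together with the withdrawal rule in Section 9.0, which is a separate matter.
- **That the rule favours acupressure.** This needs both a shorter wean under acupressure and withdrawal displaced past the last dose. The documents support neither.

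The reply does not close the gap. None of the provisions it cites says that WAT-1, delirium, dose, rescue or restart data are collected after the last dose, and none gives a common end for both arms.

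**Conclusion.** The end of follow-up is contradictory between Section 5.0 and the opening summary, Section 6.1 and the Aim 2 outcomes, and it is undefined for withdrawal, dose and restart data after the last dose. For infants on both classes, the exit time itself is ambiguous. Applied literally, the rule cuts off the Aim 2 withdrawal outcome at a time that may differ by arm.

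The effect is on the descriptive WAT-1, dose and wean-duration results, and on how retention is counted under Aim 1. No hypothesis test or power statement is affected. The size cannot be given: the documents do not say how long withdrawal may last after the last dose, how many infants take both classes, or whether the unit keeps scoring once the drugs stop. A count of lost scores would rest on an assumed number of days and on all 40 infants remaining in hospital and being scored, so none is offered. The direction of any distortion is also not established. The correction is worth making before chart abstraction begins, because it is cheap then and harder to recover later.

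**What to change.** Change data collection only; care stays as it is.

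1. In Section 5.0, separate the end of data collection from the end of drug treatment. End data collection in both arms at hospital discharge, or at transfer or parental withdrawal if earlier. Reconcile this with the opening summary, Section 6.1 and the assessment table in Section 10.0.
2. Define cessation as the last dose of the last opioid or benzodiazepine, and use that definition for exposure duration, wean duration and total dose.
3. Abstract from the chart, up to the end of data collection, the WAT-1, psCAM-ICU, RASS and FLACC scores already recorded as standard of care, with rescue doses and any restart of an opioid or benzodiazepine. State how a restart is counted in wean duration and total dose.
4. In Section 10.0, add by arm the post-cessation peak WAT-1 and the number of infants restarted, each with the number of infants still being scored.

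The cost is protocol wording and a few more days of chart abstraction per infant, with no new visit or procedure. Scores after the last dose may be sparse if the unit stops scoring, which is why the number still being scored should be reported alongside.

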6.0 Study Procedures (Design)

6.1. Interventions.

Acupressure Administration (Aim1). All participants will receive the standard non-pharmacological treatment, which may include any variety of the following treatments: rooming in, soothing touch, swaddling, skin to skin, positioning, reduced stimulation, and sound machines, as needed and tolerated. These treatments are documented by nurses in the medical record. The essential characteristics for neonatal acupuncture (Figure 3) as guided by the Near-Term Infant conceptual framework (Figure 2) are included in the delivery of this acupressure protocol.

Within 24 hours of weaning medications, one of five specialty trained advanced practice providers will apply acupressure stickers to one ear (left or right depending on access to site) in accordance with the NADA protocol acupuncture technique. Application will occur at designated points including Shen Men, Liver, and Lung: in the room with the mother; and potentially during breast feeding, holding, skin to skin contact or bottle feeds. Administrators and nurses will document the activities of the infant during acupressure placement in the medical record. Stickers will remain in place for 24 hours.

At 24 hours, skin will be assessed, and stickers will then be rotated to the opposite ear every 48-72 hours if there are no adverse effects such as skin irritation. Should skin irritation be present after the 24-hour period, the sticker applied to the opposing ear will be removed in 12 hours and skin assessed. If skin irritation continues, acupressure will be discontinued, and the participant will be withdrawn from the intervention portion of the study. Parents and health care providers of the infant will still be provided surveys to assess satisfaction and acceptability of acupressure. If no skin irritation occurs, stickers may be rotated for these participants every 12 hours. Assessment of the ear skin will be documented at the time of acupressure removal in the medical record. In accordance with previous neonatal studies that applied auricular acupressure under these guidelines (48-72 hour acupressure placement), we do not anticipate skin irritation but will continue to monitor throughout hospitalization (1, 20, 28). Acupressure will be discontinued when withdrawal symptoms measure less than or equal to 3 or less than 2 above baseline with no more than 2 rescue medication doses in 24 hours. Study participants will

receive the same assessments as non-participants and must meet the same weaning qualifications in line with the standard of care.

Acupressure Efficacy (Aim 2). As part of the standard of care, multiple metrics will be captured and compared among the intervention and control group. These include duration of opioid and/or benzodiazepine medications, duration of weaning phase, duration of mechanical ventilation, and hospital length of stay. To ensure appropriate opioid dosage comparisons, all opioid medications will be converted to morphine equivalents (mg/kg/patient); benzodiazepine medications and dosages will also be captured. Consistent with the current standard of care for infants treated in the PCICU the following assessments will be conducted: Withdrawal Assessment Tool (WAT-1) for Pediatric Withdrawal every 6 hours, Preschool Confusion Assessment Method for the ICU (psCAM-ICU) every 12 hours, Richmond Agitation-Sedation Scale (RASS) every 2-4 hours and Faces Legs Activity Cry Consolability Scale (FLACC) every 4 hours.

Acupressure Acceptability (Aim 3). Prior to discharge and after completion of the weaning protocol, parent(s) will receive the Client Satisfaction Questionnaire (CSQ8) to assess parental satisfaction of acupressure as an additional therapy. Staff and providers who cared for participants will also receive three brief electronic surveys via REDCap directly to their email prior to discharge. This survey will include 12 questions: Acceptability of Intervention Measure (AIM), Intervention Appropriateness Measure (IAM), and Feasibility of Intervention Measure (FIM) to evaluate acceptability of acupressure as a complementary therapy. Qualitative feedback back from healthcare providers and parents will be documented by administrators at time of acupressure application and skin assessment. Such feedback would include observations reported to the research team by healthcare providers or parents.

6.2. Conceptual Framework & Innovation. An important innovation of this study is the development of a standardized protocol specific for infants that is guided by the Near-Term Infant (NTI) conceptual framework to ensure that essential components of infant care are incorporated in this adjunctive treatment within the standard of care (49). To our knowledge, the use of a conceptual framework has only been implemented in one neonatal acupressure study (performed by the PI) and no consistent framework has been outlined for future studies. Use of the NTI guided the development of our acupressure protocol to ensure optimal delivery of this therapy as a complementary treatment for IWS. Based on previous evidence related to acceptability of acupressure with neonates, we will eliminate a treatment room during application, allowing the infant to be with his/her parents. An auricular technique is supported by the NTI to improve physiologic symptoms within the standard of care by reducing stimulation to the infant, as full body administration would require unwrapping, exposing body points, and laying the infant down. All of the elements defined by the NTI ensure maternal-infant bonding, as well as incorporation of family and other human interactions. These are novel elements the NADA protocol did not consider as it was developed for the adult population. Use of the NTI is innovative and significant in our study as it ensures adaptations to the NADA protocol including evidence-based strategies of acupressure that are imperative for the IWS population. Cumulatively, these considerations allow for the inclusion of acupressure within the standard of care for infants thereby promoting future feasibility and acceptance of this novel treatment by parents, health care providers, and institutions.

[figure not shown]

FIGURE 2: Near-Term Infant Conceptual Framework

FIGURE 3: Essential Characteristics for Neonatal Acupuncture as Informed by the Near-Term Infant Conceptual Framework

